### 9.2. Statistical analysis

Analyses will be fully pre-specified in a statistical analysis plan that is signed off by the Trial Steering Committee and the Trial Management Group.

Participant flow through the trial will be summarised using a CONSORT flow diagram for cluster randomised controlled trials.

Baseline characteristics of the services and participants will be described using means and standard deviations for continuous variables and numbers and percentages for categorical variables. We will report the following parameters with 95% confidence intervals that are widened to allow for clustering: % of screened people that are eligible; % of eligible people that consent to participate; % of participants that provide data at the 6-month follow-up; and % of intervention arm participants that attend at least 60% of

Page 45 of 59

scheduled sessions. To estimate these parameters, mixed logistic regression models with Satterthwaite's degrees of freedom correction will be fitted to binary outcomes that represent eligibility status, consent status, follow-up status and whether attended at least 60% of the scheduled sessions. The constant from these models will represent the log odds of the parameters which will (along with the 95% CIs) be converted to the percentage scale.

We will also report estimates of the standard deviations for continuous outcomes measured at baseline, 3 months and 6 months.

In order to assess the extent to which randomisation of clusters before recruiting participants may have resulted in recruitment bias due to the research nurses being unblinded, we will report the percentage of eligible people that participate in each of the intervention and control arms and examine the characteristics of the participants between the trial arms.

Finally, in ancillary analyses, we will report intention-to-treat estimates of the effect of the intervention on the continuous outcomes at 3 and 6 months, using 95% confidence intervals to quantify potential effectiveness. The comparison between trial arms will be undertaken by fitting mixed ("multilevel") linear regression models using Satterthwaite's degrees of freedom correction to recognise the small number of clusters in the study. Comparisons will be adjusted for the baseline score of the outcome. No p-values will be reported as it is not an objective of this study to conduct a definitive test of the intervention effect. Analyses will be undertaken using Stata software.

#### 9.3. Interim analysis and criteria for the premature termination of the trial

There are no planned interim analyses.

### 9.4. Participant population

People with dementia, over the age of 50 years old, who have had a fall in the past 6 months. Participants must be living in a private dwelling and have a family member or friend willing to take part with them.

Intention-to-treat comparisons of the outcome between the trial arms will be undertaken with participants analysed according to the trial arm their site (cluster) was randomised to. As this is a pilot study estimates from these comparisons will be reported with 95% confidence intervals only and no p values.

Page 46 of 59

### 9.5. Procedure(s) to account for missing or spurious data

Every attempt will be made to collect a complete record of data during the trial, with queries being raised for missing data to collect these within a reasonable time window if available. All data that are missing should be appropriately coded with the reason, if known, for why the data is missing.

Missing data will not be imputed for analysis. Complete case analyses of the outcome will be undertaken when comparing them between trial arms.

#### 9.6. Other statistical considerations.

Analyses will be fully pre-specified in a statistical analysis plan that is signed off by the Trial Steering Committee and the Trial Management Group. As this is a pilot study we do not anticipate marked deviations from the analysis plan. If any aspects of the analysis potentially require alteration the Trial Steering Committee will be consulted.

#### 9.7. Economic evaluation

The health economics component will test the cost-effectiveness framework within the pilot cluster RCT; it will assess collection of resource and outcome data for a future large-scale cost-effectiveness analysis (CEA). The analysis will take a societal perspective. Given potential spillover effects [24], outcomes for both the participant and their carer will be assessed (the National Institute of Health & Care Excellence (NICE) recommend that all direct health effects, whether for patients or, when relevant, carers, are included in cost effectiveness analyses [25]).

NICE guidance also recommends that cost-effectiveness analysis is undertaken using a preference-based measure (NICE 2013). Following this guidance, within the pilot RCT, we will use the EQ-5D-5L [17]. The proxy version of the EQ-5D-5L will be completed on behalf of the trial participant by their carer. The carer will also self-complete an EQ-5D-5L pertaining to their own health related quality of life (HRQoL). Both will be collected by the clinical researcher at baseline and 26 weeks. The English value set for the EQ-5D-5L recommended by NICE at the time of analysis, will be used to create index scores using the results of the EQ-5D-5L domains for each individual. The study will report the number (percentage) of partially completed and non-completed questionnaires (where the denominator is the expected number of questionnaires) and number (percentage) of missing scores due to missing individual question items for participant and carer EQ-5D-5L. Summary tables will be produced with the percentage of missing data for each of the EQ-5D-5L domains, EQ-5D index scores and EQ VAS scores for each of the time points for both participant and carer and by randomised arm.

A participant completed resource use questionnaire (HUQ) will be developed based on previous studies with similar populations [26] [15] and assessed (completion/ missing data) to collect data on health care, social care, informal care and out of pocket expenses. The questionnaires will be collected at baseline, 12 weeks and 26 weeks by the clinical researcher. The pilot RCT will also be used to hone methods of data collection for the intervention – in particular to determine the optimal

Page 47 of 59

method to collect details of the intervention delivery. In order to provide consistent results to the EQ-5D-5L outcome measures we will report the number and percentage of partially completed and non-completed HUQs (denominator expected number of questionnaires). Summary tables will be produced with the percentage of missing data for each of the HUQ cost variables for each of the time points and by randomised arm. We will also estimate the mean per patient cost over the 26 weeks duration by randomised arm. Unit costs will be obtained from a variety of sources including the Personal Social Services Research Unit [27].

# 10. Data management

#### 10.1. Data collection tools and source document identification

Data will be handled, computerised and stored in accordance with the Data Protection Act 2018. Patients' will be given a copy of their signed consent form to keep, a copy will be filed in the patients' medical notes and a copy will be filed in the investigator site file. A scanned copy will be uploaded to the secure online EDC system by site staff, in which only authorised members of the trial team will be able to access. The consent forms will be checked by an authorised member of the trial team and then deleted after the check is complete.

Paper case report forms (CRFs) designed by Exeter Clinical Trials Unit will be used to collect data which will then be input into a secure online study EDC system. CRFs will capture the date of completion and name of the person completing the CRF. The EDC system will mirror the paper CRFs and will be able to audit the users entering data, amending data and any other data changes. The eCRFs will be validated to query discrepancies in the data as well as querying missing data. SAE data will be the only exception to this method and will be entered into the EDC system directly (medical records will be used for source data). Audio recordings from qualitative interviews will be transcribed and the transcriptions will be saved as source data.

When data are captured on a CRF as the first recording of the data (e.g. participant reported outcome measures), the CRFs are the source data. Where data are accessed from medical records, the medical records will be the source data. Data on standardised outcome measures will be collected on the CRFs by clinical researchers. Data for the health economics component (HUQ) will be integrated into the CRFs. CRFs will be pseudonymised to protect the identity of the participants. Paper CRFs completed at the 6-month visits in participants' homes will be transferred to the participating site by the research nurse (or equivalent) where the data will be transcribed into the EDC system. Paper intervention CRFs will be stored securely at the relevant Trust premises and posted to Exeter CTU at the end of the intervention period. Data will then be entered into the EDC by an authorised member of the research team. Diaries will be returned to the research team at the end of the intervention. Data from the diaries will also be entered on to the EDC system.

Page 48 of 59

A clinical researcher at each site will maintain the screening log. The lists of potential patients from secondary care will include NHS/hospital number, date of birth and name and contact details to facilitate retrieval of notes and enable us to send or provide information about the study. This information will be recorded in the Investigator Site File and kept in a password protected file on a NHS Trust computer or research provider computer. The Investigator Site File will be stored in a locked room. Each patient will be allocated a unique study identifier. All data extracted from the case notes and recorded for the study will be identified only by the unique study identifier. The diagnosis of known dementia will be confirmed by the patient being on the primary care dementia QOF registers. Where the patient is not on the dementia QOF register but other information suggests they should be the GP will be asked to review the patient's Read codes and advise whether they believe the register should be revised to include the patient. For those who do not consent to be in the study the only data to be retained by the University of Exeter will be age, gender, confirmed diagnosis of dementia if confirmed and type of injury, if injury is present. For those non-participants, no patient identifiable information will be retained.

The intervention will be delivered according to manuals developed for the study with intervention documentation designed to facilitate collection of clinical data relevant to each component of the intervention. Proformas will be used by clinical staff to record baseline assessment and delivery of each component of the intervention at intervention visits. Intervention records will be returned to the research team for data extraction by secure courier services. Data will be extracted using a unique identifier and entered on to a bespoke database for analysis with an auditable data trail. The database will be held on a secure server maintained by the University of Exeter and access will be password protected.

A restricted EDC CRF will be used to store personal identifiable data (i.e. names, addresses, email addresses, telephone numbers) that will be separate from the research data. Personal data will be collected to facilitate the sharing of newsletters and study results and monitoring of consent forms by the Exeter CTU trial team and assist with retention and follow-up activities. Access to the contact details will be restricted to individuals authorised by the chief investigator. Recruiting NHS Trusts or research providers will also use the information to securely refer the participants to other NHS services or research providers involved in delivery of the study if applicable to the site.

All EDC system users will require individual log-in credentials and authorisation from an approved member of the trial management team before access is granted. The EDC system will incorporate role restriction such that individual users will only be able to access and enter or edit data as their individual permissions allow.

The Exeter CTU trial management team will run regular reports for missing data and remind sites at least monthly to enter data that is expected and document any reasons for missing data.

Healthcare professional consent forms will be signed using DocuSign provided by the University of Exeter. The qualitative researcher will have a DocuSign account with secure individual log in credentials that are not shared with other members of the study team. Completed consent forms will be downloaded and saved on a secure server with restricted access. All documents will be deleted immediately from download folders and computer recycle bins.

The study team will collect trial data on recruitment, number of sessions each participant received, details of referrals to geriatricians, type of therapist delivering intervention (OT or physio), withdrawals from the study (and reasons for this where given), and usual care services being accessed by participants. These data will be summarised to assess fidelity, feasibility, reach and dose of the

intervention for the process evaluation, and also to assess the feasibility of research processes. Where participants contact a member of the study team or clinical research nurse to withdraw from the study, permission to record the reason for withdrawal will be requested and this information will be treated as data for study records.

All audio-recordings of interviews will be fully transcribed, with identifying information such as names and locations removed. Interview transcriptions will be uploaded to NVivo, together with observation field notes. Qualitative data will be analysed using adapted thematic analysis, underpinned by a critical realist perspective. Analysis will combine a deductive and inductive approach, drawing on existing programme theory but also identifying novel factors. Analysis of implementation will be informed by Normalisation Process Theory constructs. The study qualitative researcher will keep reflexive field notes during interviews and observation, which will inform initial codes and themes in the analysis.

In a final stage of analysis, qualitative and quantitative findings will be triangulated using a joint display table, to examine implementation and mechanisms of impact in more depth. Data and findings about how the intervention operates (the process evaluation) will be kept conceptually distinct from data and findings about how well the trial and research processes operated, since these are separate research questions. Findings from the process evaluation will be used to develop a refined theory of how the intervention operates, and both sets of findings will be used to inform a definitive trial.

All data collected for the process evaluation will be stored in restricted-access computer folders on secure servers maintained by the University of Exeter.

Interviews recorded on encrypted voice recorders and any audio recordings of observations will be uploaded onto secure university folders at the earliest opportunity. After confirmation that uploads have been successful, the recordings on the voice recorder will be deleted. Where interviews are conducted on Zoom or Teams, recordings will immediately be stored in restricted-access folders on secure university servers.

Qualitative interviews will be fully transcribed. Audio-recordings and transcripts will be handled only by the qualitative team and transcribers who have signed appropriate confidentiality agreements, or by transcription companies with adequate confidentiality policies. Any recording or transcription files will be transferred to and from transcribers using a secure file transfer system. Identifying information such as names and locations will be removed from transcriptions, and an identifier code will be used to indicate the study participant, with the list of codes stored in a separate, secure file location to the transcripts. Due to the detailed nature of qualitative data, it may not be possible to fully anonymise interview transcripts (since removing too much detail can render the transcript unusable for data analysis). Folders containing transcripts will therefore only be accessed by identified research team members involved in qualitative analysis.

Audio recording files will be destroyed at the end of the study. Transcripts of interviews, observation notes and analysis files will be securely archived with the MAINTAIN study files.

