	A score of 14 or more seconds has been shown to indicate high risk of falls.	
Goal Attainment Scaling (GAS) (intervention only)	As part of the intervention, therapists will set individualised goals with participants. The goals will be agreed with the PWD by the therapists at the initial assessment and assigned 'weights'. GAS is a method of scoring the extent to which these goals are achieved in a way that is standardised for analysis [21, 22]. Progress towards goals will be measured at the final intervention visit, allowing a numerical score to be calculated at 6 months.	Baseline, 6 months
	Each goal is rated on a 5-point scale, with the degree of attainment captured for each goal area: If the patient achieves the expected level, this is scored at 0. If they achieve a better than expected outcome this is scored at: +1 (somewhat better)	
	+2 (much better)	
	If they achieve a worse than expected outcome this is scored at:	
	-1 (somewhat worse) or	
	-2 (much worse)	
	Goals may be weighted to take account of the relative importance of the goal to the individual, and/or the anticipated difficulty of achieving it.	
	Normally 3-4 goals are identified, which are incorporated into the single GAS score.	
	Overall Goal Attainment Scores are then calculated by applying a formula:	
	Overall GAS = 50 + $\frac{10 \Sigma(w_{i} x_{i})}{\sqrt{(0.7 \Sigma w_{i}^{2} + 0.3(\Sigma w_{i})^{2})}}$ Where:	
	wi = the weight assigned to the i th goal (if equal weights, wi = 1)	
	xi = the numerical value achieved (between -2 and + 2)	
	A simple spreadsheet calculator is available for use.	
Cognition assessed with mini ACE (Mini-ACE)	The Mini-ACE consists of 5 items and has a maximum score of 30	Baseline
Falls diary	Number of falls will be assessed through prospective completion of a diary during the 6 months of follow-up. Aid of an unpaid carer can be utilised if required. For each day, participants will be asked to record if they had any falls and, if so, explain the context and consequences of the fall. The data from the falls diary will be used to calculate the proportion of participants with one or more falls and the fall rate per person per year.	During the 6 months of follow up

Secondary		
Carer participants		

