#### 7.8. Quantitative assessment of falls

PWD will be asked to complete a prospective falls diary for the duration of the six month follow up period with the aid of an unpaid carer if required. These will be used to calculate:

Page 36 of 59

- the fall rate per person per year
- the proportion of participants with one or more falls
- injury and fracture rates

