### 7.9. Process evaluation and Qualitative assessment of study procedures

The process evaluation will examine implementation and the acceptability of the intervention for participants and professionals, and mechanisms of impact, including the roles of geriatricians and carer support identified in the previous study as being important. The process evaluation will be structured using a logic model, representing an initial theory of how the intervention works. Eighteen semi-structured, face-to-face interviews will be conducted with PWD receiving the intervention and their unpaid carers (paired interviews) to identify factors affecting acceptability and mechanisms of impact. Patient-carer pairs will be sampled for maximum variation, and interviews will be conducted around the end of the intervention to avoid Hawthorne effects.

Twenty-four semi-structured telephone interviews with professionals will be conducted to examine implementation, implementability (including fidelity, and mechanisms of impact, behaviour change, contextual factors). Interviews will be conducted across the 3 intervention sites and with four types of professional: geriatricians, physiotherapists, occupational therapists and support workers. During the trial delivery phase, six observations of professionals will be conducted to further investigate implementation and contextual factors. Four supervision and four multidisciplinary team meetings will also be observed. Field notes will include a reflexive perspective.

Interviews will also include questions about the acceptability and feasibility of study procedures, such as recruitment and randomisation, where professionals have been involved in these aspects of the study.

The consent process with PWD and unpaid carers will also include consent for optional participation in the qualitative aspects of the study. Interviews will take no longer than around 60 minutes and will be audio recorded with participants' permission (as documented on the initial study consent form; consent to recording will be verbally confirmed at the time of the interview).

Page 37 of 59

Maintain Study Protocol IRAS ID: 323555 Version: 3.0 Date: 08/11/2023

Table 3 Schedule of Events

	Baseline assessment (clinical researcher)	Week 1 (intervention)	Weeks 2-28 (intervention)	Week 12 follow- up assessment (clinical researcher)	Week 28 follow- up assessment (clinical researcher)
Informed consent (including consent for observation and/or interview)	X				

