#### 8. Maintain Intervention

### 8.1. Description of the Intervention

The Maintain intervention is a multidisciplinary complex intervention which is delivered in the patient participant's home. The intervention will be personalised to each participant, taking into account their physical abilities, their preference for activities and goals agreed by the therapist, the patient participant and their unpaid carer. The number of sessions the participant receives will also be tailored to their needs. The first two sessions will be assessment sessions which will be followed by up to 19 therapy sessions delivered over 12 weeks and booster sessions at 16 weeks, 20 weeks and 24 weeks. An intervention manual will detail the assessment and therapy procedures for the professionals.

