### **5. Statistical Analysis**

#### **5.1. Outcome definitions**

Feasibility Outcomes that will determine whether to proceed to full trial are as follows:

- Proportion of eligible patients consenting to pilot trial
- Proportion of participants that attend  $\geq 60\%$  of sessions as planned
- Proportion of consented participants that provide key outcome data at week 28

Pilot Randomised Controlled Outcomes are as follows:

- Activities of daily living (ADL) assessed with the Disability Assessment for Dementia (DAD) at Baseline and 28 Weeks
- European Quality of Life Instrument (EQ-5D-5L) at Baseline and 28 Weeks
- Quality of Life - Alzheimer's Disease (QOL-AD) at Baseline and 28 Weeks
- International short form Falls Efficiency Scale (Short-FES-I) at Baseline and 28 Weeks
- Timed Up and Go test at Baseline and 28 Weeks
- Goal Attainment Scaling (GAS) (intervention only) at Baseline, 12 Weeks and 28 Weeks
- Cognition assessed with Mini-ACE at Baseline
- Falls Diary assessed during the 6 months of follow up
- Carer burden assessed with the Zarit burden interview 12 (ZBI-12) at Baseline and 28 Weeks
- Carer participant quality of life assessed with the European Quality of Life Instrument (EQ-5D-5L) at Baseline and 28 Weeks
- Carer rated Patient participant quality of life assessed with the EQ-5D-5L proxy at Baseline and 28 Weeks
- Carer rated patient participant quality of life QoL-AD Proxy at Baseline and 28 Weeks
- Health and social care Utilisation Questionnaire (HUQ) at Baseline, 12 Weeks and 28 Weeks

Methods of calculation for all outcomes are defined within the protocol in Table 2.

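### Protocol 10.1 ties return of the falls diary to the end of the intervention, which does not match the six-month recording period and gives controls no return point

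*Protocol*

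**What the plan says.** **Recording period.** Four places agree, and none distinguishes the arms in its wording.
- Protocol 7.8: "PWD will be asked to complete a prospective falls diary for the duration of the six month follow up period".
- Protocol Table 2 (section 4.5): "Number of falls will be assessed through prospective completion of a diary during the 6 months of follow-up".
- SAP 5.1: "Falls Diary assessed during the 6 months of follow up".
- The Schedule of Events (Protocol Table 3) marks diary completion in week 1 and in weeks 2 to 28. It labels both columns as intervention.

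**Return of the diary.** Only Protocol 10.1 covers this: "Diaries will be returned to the research team at the end of the intervention". It gives no week and names no arm. The same paragraph treats forms from the 6-month visits separately, and says that intervention forms are "posted to Exeter CTU at the end of the intervention period".

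**Length of the intervention.** Protocol 8.1 describes "up to 19 therapy sessions delivered over 12 weeks and booster sessions at 16 weeks, 20 weeks and 24 weeks". Section 6 says that boosters run up to 6 months.

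**Follow-up.** Protocol 7.7 puts the final visit 26 weeks after the start of the intervention in the intervention arm and 28 weeks after baseline in the control arm. It does not mention collecting the diary.

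**Stopping therapy.** Protocol 7.10 lets participants withdraw from intervention delivery and from outcome assessment separately. SAP 4.3 defines a partial withdrawal as leaving the intervention while still providing data.

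**The concern.** The diary is the source for the yearly fall rate, the proportion with at least one fall, and the injury and fracture rates (Protocol 7.8). It is completed prospectively, day by day, so the date it is handed in is the last date it can cover. If sites follow 10.1 and treat the last therapy contact as the hand-over point, recording in the intervention arm could end before follow-up does, and at a time that depends on how long the person stayed in therapy. In the control arm 10.1 defines no such point, so sites would have to choose one.

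Other sources would fill little of the gap. Non-serious adverse events are not recorded, and the only serious events recorded are deaths and hospitalisations due to falls, fractures or musculoskeletal injury (Protocol 8.3). The documents name no other prospective source for falls that do not lead to admission. The SAP uses observed data only (3.3) and plans no sensitivity analyses (5.5).

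**Working it through.** The plan states no figure to reproduce. The check is how much diary time each reading of 10.1 would leave unrecorded.

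**Inputs.** Last booster at week 24 and main programme of 12 weeks (Protocol 8.1). Final visit at 26 weeks for the intervention arm and 28 weeks for controls (Protocol 7.7).

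**Formula.** Unrecorded share = (follow-up weeks − last diary week) / follow-up weeks.

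| Reading of the end of the intervention | Last diary week | Unrecorded share of 26 weeks |
|---|---|---|
| Weeks 2 to 28 column of the Schedule, i.e. up to the final visit | 26 | 0 |
| Last booster | 24 | (26 − 24)/26 = 7.7% |
| Diary taken back from someone who stops at week 12 | 12 | (26 − 12)/26 = 53.8% |
| Diary taken back from someone who stops at week 4 | 4 | (26 − 4)/26 = 84.6% |

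The last two rows are assumptions. The documents do not say when people will stop, or that the diary is taken back when they do. For a completer, ending at week 12 would contradict the booster schedule.

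SAP 2.7 gives the two follow-up times the other way round, with 28 weeks for the intervention arm. On that figure the last-booster reading loses (28 − 24)/28 = 14.3%.

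**Effect on a raw count.** Assume a constant fall rate, no true effect and no adjustment for diary time. The ratio of expected counts is then the ratio of recorded weeks. A diary ending at week 24 against a control diary of 26 weeks gives 24/26 = 0.92; against 28 weeks it gives 24/28 = 0.86. Even if both arms record to the final visit, windows of 26 and 28 weeks would give 26/28 = 0.93.

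**Would an exposure offset settle it?** SAP 5.2 specifies a mixed Poisson model, and SAP Table 16 reports an incidence rate ratio. Neither mentions diary time. An offset would correct for unequal recorded weeks if the fall rate did not depend on how long a person recorded. If person *i* falls at rate λᵢ and records for tᵢ weeks, the pooled rate is Σλᵢtᵢ / Σtᵢ. This equals the mean rate only when tᵢ and λᵢ are unrelated. If those who stop early fall more often, they contribute less time and the pooled rate is too low. No offset recovers falls that were never written down. The proportion with at least one fall also drops directly when recording is shorter.

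**The case against.** The strongest reply is that 10.1 is a sentence about handling paper. It says when diaries come back, not when completion stops, while four other places set completion over the whole follow-up. The Schedule, which sites are likely to work from, runs the diary to week 28 in a column labelled as intervention. Section 6 has boosters up to 6 months, and Table 2 treats the final intervention visit as yielding the 6-month goal score. On that reading the two points coincide and nothing is lost. People who stop therapy are covered by 7.10 and SAP 4.3, and the wording about an intervention period in the same paragraph suggests a scheduled period rather than each person's stopping date.

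Much of this stands. A reader might infer from 10.1 that falls after therapy go unrecorded, or that the intervention arm is recorded on treatment while controls are recorded in full. The documents support neither. No passage ends recording when therapy ends, and full control recording cannot be assumed when 10.1 leaves the control return point undefined. A reader might also want to put a figure on the bias. That needs a stopping proportion, a stopping time and a fall rate among stoppers, and the documents give none of these, so any such rate ratio would be purely hypothetical.

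The stakes are also limited. Falls are a secondary outcome, no progression criterion uses them (Protocol 4.4), and between-arm estimates are exploratory without p-values (SAP 3.1). Hospitalisations for falls and fractures are asked about at the 28-week visit (Protocol 8.4).

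The reply does not remove the mismatch. The only stated return rule can fall before the final visit, it does not say what happens to the diary of someone who stops early, and it cannot be applied to controls.

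**Conclusion.** The mismatch holds; a demonstrated bias does not. Section 10.1 conflicts with the recording period in Protocol Table 2, 7.8, the Schedule and SAP 5.1. For an intervention-arm completer the loss runs from zero (Schedule reading) to 2 of 26 weeks, about 8% (last-booster reading, with follow-up at 26 weeks as in Protocol 7.7). It could be larger for people who stop therapy early but stay in follow-up, and only if the diary is taken back when therapy ends, which the documents neither require nor exclude. For controls the return point is undefined. The plan therefore allows differential recording of falls in a secondary, exploratory outcome.

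One caveat: the protocol reviewed is version 3.0, while SAP section 6 lists version 5.0, and the site working instructions are not available. Whether 10.1 still reads this way should be checked first.

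**What to change.** - Reconcile Protocol 10.1 with 7.8 and the Schedule: the clinical researcher collects the diary at the final follow-up visit in both arms, whatever the therapy status.
- State that stopping or finishing the intervention does not end diary completion. It continues to the final visit unless the participant withdraws from outcome assessment.
- Record the date of the last completed diary day for each participant, and have the SAP say how recorded time enters the falls model. This also deals with any remaining difference between 26- and 28-week windows.

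The cost is a sentence or two in 10.1, the matching site instruction, one date field and one line in the SAP. The visit already takes place in both arms. If diaries have already been collected, the last diary day can be taken from the entries, and recorded time can be reported by arm and therapy status so that any shortfall is visible.
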